8.2 Serious Adverse Events

All serious adverse events (SAE) will be reported to the DCC. As per federal definitions (primarily in 21 CFR 312.32(a)), a **serious** adverse event is any adverse event that results in one of the following outcomes:

- Death
- A life-threatening event, one that places the subject at immediate risk of death (this does not include an event that, had it been more serious, would have placed the subject at immediate risk of death)
- Prolonged inpatient hospitalization or rehospitalization

UTAH One (Understanding Treatment And Health in the Ongoing coroNa Epidemic): A Hydrochloroquine Outpatient Study

- Persistent or significant disability/incapacity, indicating a substantial disruption of a person's ability to conduct normal life functions (i.e., the adverse event resulted in a significant, persistent or permanent change, impairment, damage or disruption in the patient's body function/structure, physical activities and/or quality of life).
- Important medical events that may not result in death, be life-threatening, or require hospitalization may be considered serious adverse events when, based upon appropriate medical judgment, they may jeopardize the patient and may require medical or surgical intervention to prevent one of the outcomes listed in this definition.

SAEs must be reported to the DCC within 24 hours of becoming aware of the SAE. This may be accomplished by telephone call or email and can be succinct notification.

Investigators must assess serious adverse events for expectedness and relatedness. Expected SAE include known side effects of study drug as well as clinical events consistent with worsening of COVID, or consistent with pre-existing co-morbidities of individual patients. Relatedness must be assessed by an investigator, and is based on clinical judgment that the event is related to having participated in this study. This is assessed as not related, possibly related, and related. This information must be provided to the DCC within 48 hours of becoming aware of the SAE.

Deaths from worsening of viral infection or underlying co-morbidities are expected, and do not automatically require expedited reporting. Sudden deaths or deaths believed related to cardiac arrhythmias must be reported to the DCC within 24 hours of becoming aware of the death. The DCC or medical monitor will report these deaths to the DSMB chair within 24 hours of notification. As these are expected complications of study drug, these do not require expedited reporting to the FDA or IRB as described in the next paragraph.

Serious adverse events that are unexpected and related to study participation must be reported to the FDA and the IRB within 7 days of the DCC becoming aware of the classification of the SAE. The DSMB chair will also be notified. All other SAE do not need to be reported to the IRB or FDA. All SAE will be tabulated by study arm and presented to the DSMB at its regular meetings.

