4.0 Study population

Ambulatory patients for whom SARS-CoV-2 testing is obtained at University of Utah testing sites after evaluation via telehealth services or by providers in University affiliated clinical facilities.

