8.0 Adverse Events

Patient safety is central to this study protocol.

8.1 Adverse event reporting. Adverse events will be recorded from randomization through day 14 or hospitalization, whichever occurs first. The following adverse events will be collected in the adverse event case report forms and entered into the DCC electronic data capture system:

- Serious adverse events
- Non-serious adverse events that are considered by the investigator to be related to study drug or study procedures or of uncertain relationship
- Adverse events that lead to permanent discontinuation of the study drug.

The following adverse events will be collected prospectively as part of the study-specific outcomes and do not require additional adverse event reporting with the DCC unless they meet criteria for being serious (defined below):

- Rash
- Symptomatic hypoglycemia
- Seizure
- Cardiac arrhythmias
- Worsening requirement for oxygen supplementation and support
- Nausea/vomiting
- Impaired vision

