2 STUDY OBJECTIVES AND OUTCOMES

2.1 Study Objectives

2.1.1 Primary Objective

The primary objective of the UTAH One is to assess the efficacy and safety of hydroxychloroquine (HCQ) for reduction of viral shedding and hospitalization in outpatients with confirmed COVID-19.

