7.5.2 Adverse Events

Per the protocol, AEs will be recorded through the earlier of hospitalization and Day 14.

Collected adverse events The protocol identifies adverse events (AEs) to be collected in AE report forms of the database. These include

- Serious adverse events (SAEs)
- Non-serious AEs judged by investigator as related to study drug or study procedures or of uncertain relationship
- AEs resulting in permanent discontinuation of study drug

Summaries Formal statistical analysis of adverse events is not planned, other than what has been noted previously in this SAP for adverse events that are used to define trial outcomes. However, descriptive summaries of adverse events will be created to assist the DSMB in monitoring safety.

For the closed session of DSMB meetings the overall number and percentage of patients with AEs and SAEs will be summarized, overall and by Medical Dictionary for Regulatory

Activities (MedDRA) coding. AEs will be classified by relatedness, expectedness, seriousness, intensity, action taken, outcome, and modification to study treatment. AEs will be summarized by seriousness, relatedness, and expectedness, and SAEs will be summarized by relatedness and expectedness. This will be done by treatment arm for the SAFETY population (principal focus) and for the ITT population. Generic treatment designations are preferred for interim DSMB meetings unless the DSMB requests otherwise.

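### The seriousness criteria in Protocol 8.2 leave out a first hospital admission, so some admission-causing events in this outpatient trial can miss the SAE route

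*Protocol*

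**What the plan says.** Protocol 8.2 attributes its definition to federal rules, citing 21 CFR 312.32(a), and lists five outcomes that make an event serious: death, a life-threatening event, "Prolonged inpatient hospitalization or rehospitalization", lasting disability, and important medical events. The fifth item begins: "Important medical events that may not result in death, be life-threatening, or require hospitalization may be considered serious adverse events when". It goes on to require medical judgment that intervention may be needed to prevent one of the listed outcomes.

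Protocol 8.1 names seven events (rash, symptomatic hypoglycemia, seizure, cardiac arrhythmias, worsening oxygen need, nausea/vomiting, impaired vision) that are collected as study outcomes and "do not require additional adverse event reporting with the DCC unless they meet criteria for being serious". It also fixes the recording window: "Adverse events will be recorded from randomization through day 14 or hospitalization, whichever occurs first". SAP 7.5.2 repeats the rule: "Per the protocol, AEs will be recorded through the earlier of hospitalization and Day 14".

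The study population in Protocol 4.0 is "Ambulatory patients for whom SARS-CoV-2 testing is obtained at University of Utah testing sites". The primary objective in SAP 2.1.1 is to "assess the efficacy and safety of hydroxychloroquine (HCQ) for reduction of viral shedding and hospitalization in outpatients".

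**The concern.** The hospital item suits patients who are already in hospital, whose stay can be prolonged or who can be discharged and readmitted. In an outpatient trial the usual first hospital event is an initial admission, and the item does not mention it.

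Several safeguards in Protocol 8.2 apply to an event because it is an SAE: the 24-hour notice to the DCC, the investigator's expectedness and relatedness assessment within 48 hours, the FDA and IRB report when the event is unexpected and related, and the DSMB tabulation by arm. An admission-causing event that is not classed as serious can miss them. Safety is part of the stated primary objective, so the SAE comparison between arms should not depend on whether someone chose to upgrade the event.

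**Working it through.** No arithmetic applies. The check sets the rules side by side and follows typical events through them.

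1. **Is a first admission on the list?** No. None of the five items in 8.2 names it, and no other section of either document adds it. The word prolonged is not defined. Even read as a long stay, it leaves out a short first admission.

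2. **Is the omission deliberate?** Nothing says so. The exemption in 8.1 covers seven named events, and hospitalization is not one of them. No text sets first admissions aside as endpoint events. The important-medical-event item is meant to catch events falling short of the other outcomes, and it names hospitalization among those outcomes. The list therefore presumes an item that it does not contain.

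3. **What can the hospital item capture inside the recording window?** Very little. AE recording ends at hospitalization, while prolongation and rehospitalization can only occur after an admission. The appendices do not match that stop: Appendix 1 schedules passive AE review at hospitalization, and Appendix 2 marks AE review on days 1 to 14, at day 28 and at 6 months.

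4. **Following events through the rules.** Each admission below is a brief first one. The event is not fatal, life-threatening or disabling, and is not upgraded by judgment.
   - *One of the seven events, for example a seizure.* It meets no item in 8.2, and the 8.1 exemption then means that no AE form is needed. It gets no 24-hour SAE notice, no SAE relatedness or expectedness assessment and no place in the DSMB's SAE table. The exemption overlaps with the 8.1 requirement to report related non-serious events. The text does not say which governs, so such an event can miss the form, but need not.
   - *An event outside the seven, judged drug-related or of uncertain relationship.* Under 8.1 it gets an AE form, and under SAP 7.5.2 it is summarized by relatedness and expectedness by arm. It loses the SAE label and the SAE timelines.
   - *An event outside the seven, judged unrelated.* No form is required unless study drug was permanently stopped.
   - *Worsening COVID-19.* It is not serious on the hospital item. Under 8.2 it would be expected in any case, so no FDA or IRB report would follow.

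5. **Does the discretionary item close the gap?** Not reliably. It says such events may be considered serious, not that they must be. Protocol 2.4 and 5.4 call the trial open-label, and SAP 3.3 says research coordinators are not blinded. A classification that rests on judgment could therefore differ by arm.

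**The case against.** A reader might infer that a first admission can never be an SAE, or that drug-related admissions drop out of safety reporting and survive only as an all-cause count. The documents do not support either reading.

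- An admission that is also fatal, life-threatening, disabling or prolonged is serious under 8.2. An admission for seizure or arrhythmia is also a natural candidate for the important-medical-event item.
- Related or uncertain non-serious events outside the seven still get an AE form and a causality judgment.
- Admissions are reviewed daily (Protocol 5.5), compared by arm as the 14-day outcome with chart review (SAP 5.4 and 7.3.1), and analyzed as a 28-day safety outcome in the ITT and SAFETY populations (SAP 7.5.1).
- Unanticipated problems reach the DCC within 24 hours whether or not they are SAEs (Protocol 8.3), and the DSMB may request further safety analyses (SAP 6.1).
- Because 8.2 cites the federal definition, investigators may have applied that instead of the printed bullet. The documents cannot settle this.

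All of this stands, and it limits the consequence. It does not repair the list. The unanticipated-problem route requires the event to be unexpected, so known drug risks such as hypoglycemia (Protocol 7.3) may not qualify. The hospitalization outcomes carry no relatedness or expectedness. SAP 7.5.2 names AEs and SAEs as the routine closed-session content, without a separate admission table.

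**Conclusion.** The hospital item in Protocol 8.2 is wrong as written for an outpatient trial and inconsistent with the last item of its own list. The main consequence is confined to the seven exempted events that cause a brief first admission, which can miss both the AE form and the whole SAE route. Other drug-related first admissions lose the SAE label and timelines but stay in the AE data, and every captured admission still counts in the 14-day and 28-day outcomes.

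The size cannot be given, because the documents state no admission rate. A reader might assume that 2% to 6% of 400 participants are admitted and arrive at 400 × 0.02 = 8 to 400 × 0.06 = 24 events. That range rests on assumed rates and counts admissions from any cause. The affected events are an unknown subset.

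The wording gap is certain. Actual under-reporting is only possible: it assumes that staff applied the printed list and did not use the discretionary item. The correction should be made, since it is cheap and bears directly on the SAE comparison.

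**What to change.** 1. In Protocol 8.2, replace the hospital item with one that names inpatient hospitalization, including a first admission, and prolongation of an existing hospitalization. Keep COVID-19 admissions classed as expected, as 8.2 already allows, so that they add no expedited reports. If the sponsor did mean to exempt COVID-19 admissions as endpoint events, the protocol should say so and state how they reach the DSMB by arm.
2. Reconcile the stop of AE recording at hospitalization (Protocol 8.1, SAP 7.5.2) with Appendices 1 and 2, so that the event causing the admission is itself recorded. Without this, the new item could still go unused.
3. The footnote to SAP 4.2.4 shows that enrollment has ended, so a prospective amendment alone will not help. Reclassify the admissions already found by daily review and chart review, assess relatedness and expectedness (by an assessor unaware of arm where possible), tabulate SAEs by arm under the new definition, and state in the report which definition was used.

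The cost is one SAE form and one causality assessment per admission, in a number that the documents do not give. Any reclassified event found to be both unexpected and related would also fall under the existing 7-day report to the FDA and IRB. No new participant procedures are needed.

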8.3 Unanticipated Problems

Investigators must also report Unanticipated Problems associated with the study drug or study procedures to the DCC within 24 hours. An unanticipated problem is any incident, experience, or outcome that meets all of the following criteria:

- Unexpected, in terms of nature, severity, or frequency, given the research procedures that are described in the protocol-related documents, such as the IRB-approved research protocol and informed consent document; and the characteristics of the subject population being studied;
- Related or possibly related to participation in the research. Possibly related means there is a reasonable possibility that the incident, experience, or outcome may have been caused by the procedures involved in the research; it is not intended to identify the event as possibly related imply because it cannot be proven to be unrelated.

UTAH One (Understanding Treatment And Health in the Ongoing coroNa Epidemic): A Hydrochloroquine Outpatient Study

- Suggests that the research places subjects or others at a greater risk of harm (including physical, psychological, economic, or social harm) than was previously known or recognized.

9.0 Miscellaneous Topics

9.1 Reporting and Regulatory Compliance.

All relevant information will be reported in compliance with relevant regulations and Good Clinical Practice. This is not a registrational trial but will be performed under an IND exemption.

9.2 ClinicalTrials.gov registration.

This trial is registered with ClinicalTrials.gov (NCT04342169). Updates to the Clinicaltrials.gov entry will be made in compliance with relevant regulations.

9.3 Records retention. Study sites will arrange for the retention of raw data as per institutional protocol but for a minimum of 3 years after publication of the primary paper. All data and documents will be made available when requested by appropriate authorities. Records will be maintained to verify the existence of each patient in the study, as per standard protocol.

UTAH One (Understanding Treatment And Health in the Ongoing coroNa Epidemic): A Hydrochloroquine Outpatient Study

APPENDICES

Appendix 1. Visit schedule

Procedure	Visit					
	Baseline	Daily through 15 days	14 days	Hospitalization	28 days	6 months
Screening procedures	X					
Informed consent	X					
Data collection	X	X	X	X	X	X
Active Adverse Event review		X				
Passive Adverse Event review				X		
EQ-5D-5L, PHQ-9, GAD 7, PLC 5	X				X	X

EQ-5D-5L: EuroQol-5 dimensions-5 level; PHQ-9: Patient Health Questionnaire-9, GAD 7: Generalized Anxiety Disorder 7-item scale, PLC 5: PTSD Checklist for DSMB-5 scale

UTAH One (Understanding Treatment And Health in the Ongoing coroNa Epidemic): A Hydrochloroquine Outpatient Study

Appendix 2: Biospecimen collection schedule:

Study Events	Day	0	1	2	3	4	5	6	7	8	9	10	11	12	13	14	28	6 months
		HCQ or Placebo																
COVID-19 PCR swab positive		1																
Inclusion / Exclusion criteria		1																
Informee consent discussion / signatures		1	1															
Adverse event review			1	1	1	1	1	1	1	1	1	1	1	1	1	1	1	1
Surveys (EQ-5D-5L / PHQ-9 / GAD7 / PLC5)				1													1	1
HCQ or Placebo administration				1	1	1	1	1										
Research Specimen Collection																		
Oropharyngeal self-swab for SARS-CoV-2			1	1	1	1	1	1	1	1	1	1	1	1	1	1	1	
Household contact over age 18 oropharyngeal self-swab for SARS-CoV-2			1	1	1	1	1	1	1	1	1	1	1	1	1	1	1	
Peripheral blood (PBMC / plasma biobank)	40 mL (five yellow top ACD tubes)		1						1								1	1

- Section 2.1.3: Included two additional core symptoms (chills and diarrhea).
- Section 5.4: Modified definition of symptom duration and start/end dates. Restricted to individuals symptomatic at baseline. Applied censoring at 15 days rather than using symptom assessments through 28 days because there is not daily symptom information after Day 15 (different from protocol). Added details for post-imputation processing of certain values for participants missing some assessments because they were deceased when the assessment was to have been administered.
- Section 7.4: Removed analysis of numerical viral shedding values.
- Section 7.4.5: Updated imputation approach and analytical methods of the EQ-5D-5L assessments (and subsequent assessments).

Batch of changes for preliminary version of 16 July 2020

- Signature Page: Restricted to PIs and trial statisticians, removing the clinical data manager line as this was deemed unnecessary.
- Section 2.1.3: Changed a secondary outcome from “Duration of viral shedding, measured on days 1 - 14 and 28” to “Persistence of viral shedding on day 28.” The secondary outcome had essentially been the primary outcome with one later measurement and as such duration is not accurately captured beyond what is available in the primary outcome. The replacement secondary outcome maintains complementary status with the primary outcome and is straightforward.

- Section 4.2.4: Changed the statement that the ITT population “will be the primary population for most efficacy and safety analyses” to “will be the primary population for efficacy analyses.”
- Section 4.2.5: Changed wording re sensitivity analyses of efficacy outcomes on the dITT population from stating they will be conducted to stating they may be conducted. Also clarified that the dITT population is restricted to subjects who are delivered the assigned study drug.
- Section 4.2.7: Defined the safety population to require only one pill/tablet of the delivered study drug to be administered, and that the arms for the SAFETY population are based on what was delivered rather than what was assigned, in case there are discrepancies. Previously the principal safety population for adverse events not already described as an outcome was the per-protocol population.
- Section 5.4: Added definition of assessment days and defined how to handle drug days and assessment days if the anchoring events (drug delivery and assessment surveys) are not available. Corrected censoring explanation for symptom duration to censor on last *symptomatic* day, as applicable. Added definition of comorbidity presence/absence.
- Section 7.1: Added the SAFETY population as a component of the CONSORT-like diagram. Clarified that footnotes may be used to describe some populations.
- Section 7.3.2: Modified to include all 15 daily assessments in defining the univariate average symptom level outcome. Further restricted imputation and analysis to individuals who are not known to have been hospitalized or died on or before *DayA15*, and who have at least one day with a non-missing average symptom level for *DayA1–DayA15*. Previous restriction had specified those not meeting the primary outcome or died within 14 days.
- Section 7.3.3: Moved what had been described in Section 7.4 as *Viral shedding at DayD28* to this section. This reflects the substitution of a secondary outcome from *viral shedding duration through Day 28* to *persistence of viral shedding on day 28*.
- Section 7.4.1: Added a sensitivity analysis for symptom duration that assumes symptom resolution on the first asymptomatic day, regardless of subsequent symptom levels. Also emphasized the departure from the originally specified outcome in the protocol which also considered the Day 28 measurements.
- Section 7.4: Reinserted numerical viral shedding values as an exploratory outcome and described a tentative analysis plan.
- Section 7.5: Stated when safety (rather than per-protocol) and intent-to-treat populations would be used for safety analyses.

Batch of changes for preliminary version of 22 July 2020

- Section 2.1.3: Explained the change from a secondary outcome of *Duration of viral shedding, measured on days 1-14 and 28* to *Persistence of viral shedding on day 28*.
- Sections 5.4, 7.3.3: Described when and how missing Day 28 viral shedding values will be assumed positive or negative, with other values imputed unless the participant has died on or before *DayR + 30*. Explained there is a window for obtaining the Day 28 swabs.
- Section 5.4: Adjusted the definition of the adult household acquisition variable to replace “test” with “swab,” assuming only the outcome of study-associated swabs will be systematically collected in the database. Also, changed from considering results “at any time” to looking at the results of the collected swabs because it is unclear that tests other than from non-study swabs will be available, and there is a bounded interval for when study swabs are to be collected.
- Section 7.3.2: Made the restriction less narrow to not exclude subjects who were hospitalized or who died on or before *DayA15*. Described how the last value carried forward approach will be used in conjunction with multiple imputation.
- Section 7.2.1: Clarified that the restricted mean duration and median duration analyses of the primary outcome will be stratified by *age group*. Explained how the confidence intervals will be created via nonparametric-bootstrap resampling and empirical percentiles.
- Section 7.4: Removed the viral shedding numerical outcome analysis paragraph (and from the list in Section 5.4).

Batch of changes for preliminary version of 27 July 2020

- Section 5.4: Clarified how assessment days after *DayA1* are defined. Also noted that “swab days” are intended to align with drug-delivery days, and that like assessment days, a window is allowed for the *DayD28* measurements.

Batch of changes for preliminary version of 28 July 2020

- Section 5.4: Clarified what to do if there are multiple daily averages on the same calendar day or if there are multiple swabs on the same calendar day. Affects the definition of the viral shedding duration (the primary outcome), the average symptom level (a secondary outcome), the persistence of viral shedding on day 28 (a secondary outcome), and the symptom duration (an exploratory outcome).
- Section 5.4: Amended the definition of the primary outcome to clarify that swabs after *DayD14* are ignored when defining the primary outcome, even for purposes of confirmation of an earlier negative result.

- Section 5.4: Edited the first sentences describing the persistence of viral shedding on day 28 outcome to emphasize this is an outcome that replaced the originally specified outcome of viral shedding duration from days 1-14, 28.
- Section 7.4: Added a note about a possible exploratory analysis for numerical viral shedding measurements. The note was added to reconcile why the analysis of this exploratory outcome is not described in the current version of the SAP, despite the inclusion of such language in the original protocol.

Batch of changes for preliminary version of 29 July 2020

- Section 5.4: Defined several distinct outcomes for adult household contact viral acquisition. The main such outcome is now at the household level rather than at the person level. Additional outcomes are at the person level, as a dichotomous outcome and as a count outcome. These household contact acquisition outcomes, and the analysis methods applied to them, are still subject to change after consulting with an experienced infectious disease modeling person and better understanding incoming data.
- Section 7.3.2: Clarified Step 4 for post-processing of imputed values on hospitalized days.
- Section 7.4.1: Inserted a missing word, “a,” in the first sentence.

Batch of changes for preliminary version of 03 August 2020

- Section 5.2: Added: “When multiple imputation is employed, it will be performed separately within each treatment arm if possible (by ITT arm for analyses of the ITT population or subpopulations thereof, or, if necessary, by SAFETY arm for analyses of the SAFETY population).”
- Section 7.3.2: Instead of including treatment as a variable in the imputation model, specified that imputation will be by treatment arm.
- Section 7.3.2: Added the last paragraph to clarify that the principal analysis for the average symptom level outcome is on the same set of subjects who are included in the imputation model for this outcome.
- Section 7.3.3: Added to the imputation model for the viral shedding at Day 28 outcome the following qualifier for the inclusion of a treatment arm indicator: “(if imputation is not already stratified by treatment arm)”.

Batch of changes for preliminary version of 07 November 2020

- Section 5.4: Changed text to assume that collected surveys/swabs pertain to the intended day. As such removed text pertaining to assessments/swabs collected on the same calendar day. (Supersedes changes from 28 July 2020.)

- Sections 5.4 and 7.3.4: Clarified for the adult household viral acquisition outcome that it considers swabs from adult household contacts (rather than also considering swabs from the index subject).

Batch of changes for preliminary version of 11 November 2020

- Section 5.4: Changed text to assume that collected surveys/swabs pertain to the intended day for surveys, but to the participant-reported collection date for swabs. (Supersedes changes from 07 November 2020.) Added specific language about permissible windows for surveys and for “day 28” swabs.

Batch of changes for preliminary version of 13 November 2020

- Section 5.4: Removed redundant language about swab collection dates being per participant report, and corrected one reference to swabs that was supposed to refer to surveys.

Batch of changes for Version 1 of 18 November 2020

- Updated study name/acronym and latest protocol version number/date.
- Removed all references to the SAP version being preliminary.
- Section 7.5.2: Changed language from closed session of DSMB meetings being “tentatively planned for after approximately 100, 200, 300, and all subjects have been enrolled” to “tentatively planned for after approximately 100, 300, and all subjects have been enrolled.” Within the last week, the DSMB meeting scheduled for November 30th was postponed. Nearly 200 were enrolled as of the accompanying October screen cutoff date that would have been used if the meeting were to take place November 30th. With a new tentative target of mid- to late-January for the next DSMB meeting, enrollment may be near 300.

Batch of changes for Version 1.1

- Section 5.4: Removed “, with the day 28 wording asking about the past two weeks” because the day 28 symptom assessment asks about one day, not for the past two weeks.
- Section 5.4: Corrected the erroneous statement about the symptom duration exploratory outcome: “Therefore, the *DayA15* assessments asking about symptom levels over the previous two-week period will be ignored.” It now states, “Therefore, the *DayA28* symptom assessments will be ignored when determining symptom duration.”
- Section 7.5.2: Removed the phrase “(tentatively planned for after approximately 100, 300, and all subjects have been enrolled)” in describing the closed session of DSMB meetings. The change of 18 November 2020 to remove “200” as a planned frequency

should not have been made as the meeting postponement was not intended to reduce the number of meetings, but rather to delay one meeting. The DSMB charter describes the ability of the DSMB to have flexibility in the frequency of meetings. The removed text is not necessary for the SAP, regardless.

- Corrected page headers to state “Statistical Analysis Plan” instead of “Provisional Draft of Statistical Analysis Plan for Internal Review.”
- Cover page: Noted that September 24, 2020 is the effective date (in this case, also the IRB approval date) for version 1.5 of the protocol. Added prior protocol version numbers and effective dates. Added the effective date for version 1.0 of the SAP.

Batch of changes for Version 1.2

- Cover page: Added approval date for SAP Version 1.1 and creation date for SAP Version 1.2.
- Sections 5.4 and 7.3.4: Amended the adult household contact viral acquisition outcomes to be based on collected swabs *through Day D14* for the main analysis. Previously these outcomes had been defined using all collected swabs. Noted additional exploratory analyses that modify the revised outcomes to also include the Day 28 swabs, as before.
- Section 5.4. Changed “will” to “may” in the following excerpt to make the outcome optional: “Another person-level outcome will–may count the number of study-administered positive swabs from the person and the number of study-administered swabs with a result . . .”
- Section 5.4: Added a missing closing parenthesis to the definition of the EQ-5D-5L VAS.

Batch of changes for Version 1.3

- Cover page: Added approval date for SAP Version 1.2 and creation date for SAP Version 1.3. Updated the current protocol version to 1.6 and added its effective date. Noted use of some DCC language and contributions from [name].
- Section 2.1.3: Instead of stating the protocol will be amended, noted that the protocol has been amended to include persistence of viral shedding at Day 28 as a secondary outcome.
- Edited the wording and definition of the primary outcome to better align with the protocol. Changes are noted with strikethrough (deleted text) and italics (new text) in the following:
 - Section 2.1.2: “The primary outcome is duration of viral shedding, as defined by days from randomization to the first of two consecutive negative swabs, measured ~~on days 1–14 through 14 days after randomization~~ (formally defined in Section 5.4).”

- Section 5.4: “Duration of viral shedding (~~until DayD14 through 14 days after randomization, i.e., DayR + 14~~: this is an integer outcome which is defined as (Date of first sustained negative swab (*ignoring any swab that was not in the interval DayR + 1 through DayR + 14, inclusive*) - DayR). The date of first sustained negative swab is the first day with a negative swab followed by the next available day’s swab being negative. The requirement for confirmation will be waived for patients who are negative for shedding on *DayD14* *DayR + 14*. If no more positive swabs nor negative swabs are available ~~by DayD14 by DayR + 14~~ following a negative swab, the date of the negative swab will be considered confirmed for the primary analysis (using the last-observation-carried-forward approach). If the final swab from on or before *DayD14* *DayR + 14* which has a positive or negative result is positive and there were not two preceding consecutive negative swabs, the duration will be considered to be right censored on the day of the positive swab.”
- Section 7.2: “Due to the nature of the data collected over the *DayR*–(*DayR + 14*) *DayD14* interval, and uncertainty about the distribution of shedding duration and the resulting hazard function, our primary analysis will apply the stratified log-rank test to compare the distribution of shedding duration between the hydroxychloroquine and control groups, with administrative right censoring at *DayD14* *DayR + 14*.”
- Section 7.2.1: “For example, in the unexpected scenario where the cumulative incidence curves for the ending of shedding actually cross during the *DayR*–*DayD14* (*DayR + 1*) to (*DayR + 14*) evaluation period”.

- Section 5.4: Edited the wording and definition of a secondary outcome to better align with the new definition of the primary outcome: “The protocol originally specified a secondary outcome of duration of viral shedding for days 1–14 and 28. Because the primary outcome is viral shedding ~~through Day 14 from DayR + 1 through DayR + 14~~, the secondary outcome of persistence of viral shedding on Day 28 is substituted for duration through Day 28; there is limited precision between Days 15 and 28. The definition of the persistence of viral shedding on Day 28 outcome relies heavily on the Day 28 swab and is limited to those who have a test result for the Day 28 swab or who are not known to have died on or before *DayR + 30* (there is a ± 2 day window for collecting the Day 28 swab). If the Day 28 swab result is known, the result will be used to define the outcome (“yes” if positive, “no” if negative). Otherwise, subjects with a confirmed cessation of viral shedding ~~by Day 14 when considering daily swab results from DayR + 1 to DayR + 25, inclusive (with the requirement for confirmation waived if the latest available daily result in this interval is negative)~~, and a missing Day 28 value will be assumed to be negative on Day 28; otherwise subjects hospitalized on any of the days *DayR + 26*–*DayR + 30* with a missing Day 28 value will be assumed to

be positive on Day 28; otherwise, multiple imputation will be performed as described in Section 7.3.3.”

- Edited the wording and definition of another secondary outcome to better align with the new definition of the primary outcome.
 - Section 5.4: “**Adult Household Contact Viral Acquisition** This outcome will be analyzed for households with at least two adults for which no other adult besides the index study subject is positive for COVID-19 at baseline and for which the index study subject is in the ITT population. This binary outcome will be at the household level and will be a “yes” if there is a positive swab by one or more adult household contacts for any of the study-administered swabs ~~through DayD14 (i.e., not including Day 28 swabs) from days DayR + 1 to DayR + 14, inclusive.~~ If there are no positive swabs but at least one negative swab, the outcome will be a “no;” otherwise it will be missing. For some additional analyses, an analogous outcome will be defined at the person level for each non-index adult from a household for which no other adult besides the index study subject is positive for COVID-19 at baseline and for which the index study subject is in the ITT population. Another person-level outcome may count the number of study-administered positive swabs from the person and the number of study-administered swabs with a result (e.g., as an offset in a Poisson regression model), again ~~through DayD14 from days DayR + 1 to DayR + 14, inclusive.~~
 - “As exploratory outcomes, the definitions in the previous paragraph will also include ~~the Day 28 swabs (i.e., all study-administered swabs).~~ *study-administered swabs after DayR + 14 through DayR + 30, if available.*”
 - Section 7.3.4: “The analyses in this paragraph will be conducted twice, once when using the principal version of the outcomes (i.e., using swabs collected ~~through DayD14~~ from DayR + 1 to DayR + 14, inclusive) and once when using the additional exploratory versions of the outcomes (i.e., using all collected swabs; and therefore also including ~~Day 28 swabs from DayR + 1 to the Day 28 swabs, inclusive~~).
